7.2. Participant Withdrawal from the Trial

In accordance with the Declaration of Helsinki (and in accordance with the applicable country's acceptance), each participant is free to withdraw from the trial at any time. The Investigator also has the right to withdraw a participant from the trial for any reason. Reasons for participant withdrawal include but are not limited to the following:

1. Participant withdraws consent or requests discontinuation from the trial for any reason.
2. Participant develops an AE that would interfere with his/her continued participation.
3. Participant is noncompliant with the trial procedures and assessments or administration of IMP in the opinion of the Investigator.
4. Confirmed pregnancy in a female participant.
5. The Sponsor requests withdrawal of the participant.
6. Participant experiences an AE or other medical condition that indicates to the Investigator that continued participation is not in the best interest of the participant.

Participants should be treated with standard of care after withdrawal from the trial as appropriate.

If a participant withdraws consent, every attempt will be made to determine the reason. For participants withdrawn from the trial, all efforts will be made to complete and report all observations up to the time of withdrawal. EOT procedures should be completed at the time of the participant's withdrawal (assuming consent is not withdrawn) and an explanation given as to why the participant is withdrawing or being withdrawn from the trial. Participants who discontinue during treatment period 3 should be encouraged to also complete the EOT visit on day R84.

If the reason for withdrawal is an AE and/or a clinically significant abnormal laboratory test result, monitoring will be continued at the discretion of the Investigator (eg, until the event has

resolved, stabilized, or returned to baseline; until the participant is referred to the care of a health care professional; or until a determination of a cause unrelated to any of the IMPs or trial procedure is made). The specific event or test result (including repeated test results, as applicable) must be recorded both on the source documentation and in the CRF. If the Investigator determines that the AE is related to the IMP, monitoring should continue until the AE has resolved or stabilized.

The Investigator must inform the clinical trial physician/clinical leader as soon as possible of all participants who are being considered for withdrawal due to AEs. Additional reports must be provided when requested.

7.3. Lost to Follow-up

A participant will be considered lost to follow-up if they repeatedly fail to return for scheduled visits and are unable to be contacted by the investigational center. The following actions must be taken if a participant fails to return to the investigational center for a required trial visit:

- The investigational center must attempt to contact the participant and/or the participant's caregiver and reschedule the missed visit as soon as possible and counsel the participant on the importance of maintaining the assigned visit schedule and ascertain whether or not the participant wishes to and/or should continue in the trial.
- In cases in which the participant is deemed lost to follow-up, the Investigator or designee must make every effort to regain contact with the participant and/or the participant's caregiver in accordance with the clinical site standard procedures. These contact attempts should be documented in the participant's medical record.

Should the participant and the participant's caregiver continue to be unreachable, the participant will be considered to have withdrawn from the trial with a primary reason of "lost to follow-up."

7.4. Trial Stopping Rules

The Sponsor may suspend or terminate the trial in the event of:

- new toxicological or pharmacological findings or safety issues that invalidate the earlier positive benefit-risk assessment
- discontinuation of the development of the IMP
- an SAE of interest considered by the Principal Investigator and/or Sponsor as related to the IMP

If 3 or more participants meet stopping rules criteria during the trial, as described below, the Investigator, clinical lead, clinical trial physician, and pharmacovigilance physician will meet to decide on the need for trial discontinuation:

- drug-induced liver injury
- any drug-related SAE
- any CTCAE Grade 3 laboratory test result, or a CTCAE Grade 2 laboratory test result lasting over 48 hours, graded according to the National Cancer Institute (NCI)

CTCAE, version 5.0. An exception to that rule is isolated Grade 3 hypophosphatemia.

At any time during the trial, and after discussion between the Sponsor and Investigator, the trial may be stopped, if the following occur:

- previously unknown data that raise concern about the safety of the trial participants become available, and
- following administration of 1 of the olanzapine extended-release formulations, 3 or more participants (cumulative across the trial, from all cohorts) meet the definition of PDSS.

Any possible symptoms of a PDSS event will be monitored based on establishing evidence for all 5 criteria in the definition for a clinical diagnosis of a PDSS as described in Section 8.3.8 (adapted from [Detke et al 2010](#)).

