1. Cohort 1: Olanzapine for Extended-release Injectable Suspension D (TV-44749) (Fast-D)
2. Cohort 2: Olanzapine for Extended-release Injectable Suspension (TV-44749) (to-be-marketed)
3. Cohort 3: Olanzapine for Extended-release Injectable Suspension C (TV-44749) (Slow-C)

The aim is to achieve approximately 20 completers in each cohort. Period 3 will be initiated with a sentinel cohort 1A (Fast-D) composed of approximately 2 to 4 participants. A safety review committee (SRC) composed of the Sponsor's clinical trial physician, clinical leader, PV physician, and other relevant experts, will be summoned to review all safety data (including demography, vital signs, clinical laboratory tests, ECGs, adverse events (AEs), concomitant medications local tolerability and pain, leakage assessment) available upon completion of the first 15 days of the sentinel cohort (day R1 to day R15, inclusive) (cohort 1A). The sentinel cohort will serve for initial evaluation of the systemic safety and tolerability of the Fast-D formulation. Participants assigned to cohort 1A will be in an inpatient setting for 15 days following administration of the Fast-D formulation, to allow safety review prior to dosing of the rest of the Fast-D cohort (cohort 1B).

For cohort 1B (n~16 participants), period 3 may be initiated only following SRC decision. Randomization to cohort 2 (n~20 participants) and cohort 3 (n~20 participants) will be initiated in parallel to cohort 1B. If no safety concern is raised from review of data from cohort 1A, the inpatient period of cohorts 1B, 2, and 3 will be identical and will include an inpatient period of 3 days (day R1 to day R3) followed by a 25-day outpatient period (day R4 to day R29).

Period 3 will include PK blood sampling and safety assessments ([Table 3](#) and [Table 4](#)).

In the case that a safety concern arises following a review of the safety results from cohort 1A, or one of the stopping rules in participants as detailed below ([Section 7.4](#)) is met, the following may be considered:

- Adjust the olanzapine extended-release sc dose
- Pause olanzapine extended-release sc dosing until additional data become available
- Maintain the inpatient period of cohort 1B as in cohort 1A
- Modification of the inpatient period of cohorts 1A and 1B to up to 28 days for close safety monitoring
- Stop the trial

At any time, the SRC may request additional evaluation including PK data before allowing continued dosing.

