9.5. Safety Analyses

Safety analyses will be performed on the safety analysis set (Section 9.1.3). No formal statistical analyses of safety data are planned. The safety analysis will be performed by any of the IMPs (ZYPREXA im or sc olanzapine).

For continuous variables, descriptive statistics (n, mean, standard deviation, standard error [SE], median, minimum, and maximum) will be provided for actual values and changes from baseline to each time point. For categorical variables, participant counts and percentages will be provided.

If any participant dies during the trial, a listing of deaths will be provided, and all relevant information will be discussed in the participant narrative included in the CSR.

Subjective overall tolerability will be assessed by calculating the number (%) of participants who failed to complete the trial, and the number (%) of participants who failed to complete the trial due to AEs.

The use of concomitant medications and rescue medications will be summarized by therapeutic class for each treatment and cohort using descriptive statistics.

The analyses will include the following data:

Adverse Events: All AEs will be coded using the Medical Dictionary for Regulatory Activities (MedDRA). Each participant will be counted only once in each preferred term (PT) or system organ class (SOC) category for the analyses of safety. Summaries will be presented for all TEAEs and adverse device events (overall and by severity), including AEs determined by the Investigator to be related to IMP and/or medical device (defined as related or with missing relationship), SAEs, serious device adverse events, and AEs and adverse device events causing withdrawal from the trial. Summaries will be presented by treatment and cohort for all participants. Participant listings for TEAEs and adverse device events that are serious and those leading to withdrawal will be presented.

PDSS events (as defined above in the stopping criteria) and ISRs of pus-containing lesions (abscess, infection, or inflammation), ulceration, necrosis, and atrophy will be subject to expedited reporting.

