10.2. Committees

An SRC composed of the Sponsor's clinical trial physician, clinical leader, PV physician, and other relevant experts will be summoned to review all safety data available upon completion of the first 15 days of the sentinel cohort (cohort 1A).

In the case of a suspected PDSS event, an adjudication committee composed of the Sponsor's clinical trial physician, clinical leader, PV physician, pharmacometrist, and other relevant experts, such as a statistician and a PK expert, will be summoned to review all cases of suspected PDSS to determine if each case fulfills all 5 criteria in the definition for a clinical diagnosis of PDSS (adapted from [Detke et al 2010](#)), as well as to evaluate the robustness of the available clinical evidence. An external independent physician with expertise in the relevant therapeutic area may be consulted, if needed.

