1. Cohort 1: Olanzapine for Extended-release Injectable Suspension D (TV-44749) (Fast-D)
2. Cohort 2: Olanzapine for Extended-release Injectable Suspension (TV-44749) (to be marketed)
3. Cohort 3: Olanzapine for Extended-release Injectable Suspension C (TV-44749) (Slow C)

The aim is to achieve approximately 20 completers in each cohort. Period 3 will be first initiated with a sentinel cohort 1A (Fast-D) composed of approximately 2 to 4 participants. A safety review committee (SRC) composed of the Sponsor's clinical trial physician, clinical leader, PV physician, and other relevant experts, will be summoned to review all safety data (including demography, vital signs, clinical laboratory tests, ECGs, adverse events (AEs), concomitant medications local tolerability and pain, leakage assessment) available upon completion of the first 15 days of the sentinel cohort (day R1 to day R15, inclusive) (cohort 1A). The sentinel cohort will serve for initial evaluation of the systemic safety and tolerability of the Fast-D formulation. Participants assigned to cohort 1A will be in an inpatient setting for 15 days following administration of the Fast-D formulation, to allow safety review prior to dosing of the rest of the Fast-D cohort (cohort 1B).

For cohort 1B (n~16 participants), period 3 may be initiated only following SRC decision. Randomization to cohort 2 (n~20 participants) and cohort 3 (n~20 participants) will be initiated in parallel to cohort 1B. If no safety concern is raised from review of data from cohort 1A, the inpatient period of cohorts 1B, 2, and 3 will be identical and will include an inpatient period of 3 days (day R1 to day R3) followed by a 25-day outpatient period (day R4 to day R29).

Period 3 will include PK blood sampling and safety assessments (Table 3 and Table 4 of the trial protocol).

In the case that a safety concern arises following a review of the safety results from cohort 1A, or one of the stopping rules in participants as detailed below (Section 7.4 of the study protocol) is met, the following may be considered:

- Adjust the olanzapine extended-release sc dose
- Pause olanzapine extended-release sc dosing until additional data become available
- Maintain the inpatient period of cohort 1B as in cohort 1A
- Modification of the inpatient period of cohorts 1A and 1B to up to 28 days for close safety monitoring
- Stop the trial

At any time, the SRC may request additional evaluation including PK data before allowing continued dosing.

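### Protocol 7.4 joins its last two stopping conditions with *and*, so read literally three PDSS cases do not meet that rule by themselves; the practical gap is PDSS that is nonserious or not judged drug-related

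*Protocol*

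**What the plan says.** Protocol 7.4 contains three lists.

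- **First list.** The Sponsor may suspend or terminate for "new toxicological or pharmacological findings or safety issues that invalidate the earlier positive benefit-risk assessment", if development of the product stops, or for an SAE of interest that the Principal Investigator or Sponsor considers related.
- **Second list.** If three or more participants meet its criteria (liver injury, any drug-related SAE, or specified laboratory grades), the Investigator, clinical lead, clinical trial physician and pharmacovigilance physician will meet to decide whether to discontinue the trial.
- **Last list.** After Sponsor and Investigator confer, "the trial may be stopped, if the following occur". Its first bullet is "previously unknown data that raise concern about the safety of the trial participants become available, and". Its second is that, after an extended-release injection, "3 or more participants (cumulative across the trial, from all cohorts) meet the definition of PDSS".

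Other sections rely on these rules or bear on PDSS. Protocol 4.1 lists five actions that may be considered: adjust the dose, pause dosing, keep cohort 1B inpatient as in 1A, lengthen the inpatient stay, or stop. They open if the cohort 1A review raises a safety concern, or if "one of the stopping rules in participants as detailed below" is met; SAP 2.1 says the same. Under 8.4.8.1, PDSS is an event of special interest that may be serious or nonserious. Under 10.2 a committee "will be summoned to review all cases of suspected PDSS to determine if each case fulfills all 5 criteria". Section 7.1 makes a confirmed event a reason to discontinue the individual, and 10.5 lets the Sponsor end the trial for any reason.

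Section 8.3.8 is redacted and Table 8 is not shown. Nothing is assumed about either; 7.4 cites 8.3.8 for the PDSS definition.

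**The concern.** The lead-in to the last list has no *any of* or *either*, and the bullets are joined by *and*. The plain reading is that both conditions must hold. A count that looks like a PDSS stopping threshold then fails to work as one: a third PDSS case would not meet the rule until someone also established that previously unknown safety data had become available.

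This matters because the count is the only trial-level PDSS threshold in the visible text. The Protocol synopsis does not expect the safety review committee to monitor safety beyond its cohort 1A review. After that review, the 7.4 rules are the only trigger that Section 4.1 names for considering its five actions. Adjudication under 10.2 classifies each case but attaches no trial-level consequence to a number of cases.

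**Working it through.** The check is logical; no rate or sample size enters. The plan states no operating characteristics for this rule, so there is no figure to reproduce.

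**Step 1: what the connector does.** Let A be that previously unknown safety data become available, and B that three or more participants meet the PDSS definition. Three wordings are compared: the text as written, a version in which B suffices and A alone does not, and a plain *or*.

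| A | B | *and* (as written) | B sufficient alone | *or* |
|---|---|---|---|---|
| no | no | not met | not met | not met |
| no | yes | **not met** | met | met |
| yes | no | not met | not met | **met** |
| yes | yes | met | met | met |

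The rule is met in 1 of 4 combinations as written, 2 of 4 if only the PDSS count is made sufficient, and 3 of 4 with *or*. Moving from *and* to *or* changes two rows: B without A, which is the problem, and A without B, which is a side effect.

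**Step 2: what the rest of 7.4 already catches.** Take the row B without A and ask whether another list applies to the PDSS cases.

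| PDSS cases in three participants | Second list (three with a drug-related SAE) | First list (related SAE of interest) |
|---|---|---|
| All serious and judged related | met; the named roles will meet | available from the first case |
| Two serious and related, one nonserious | 2 of the 3 needed, unless another participant meets a criterion in that list | available from the first serious related case |
| All nonserious | not met | not available |
| All serious, none judged related | not met | not available |

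The first-list column assumes that a serious related PDSS case counts as an SAE of interest. The term is not defined in 7.4, but PDSS is a protocol-defined event of special interest in 8.4.8.1. The first list also has the benefit-risk item, which could apply in any row but is a judgement with no count.

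The uncovered cases are therefore those that are nonserious or not judged drug-related.

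**Step 3: what Section 4.1 adds.** Its five actions have two alternative triggers. A safety concern from the cohort 1A review opens all five without any 7.4 rule being met. After that review, a 7.4 rule can also be met through the first or second list.

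**The case against.** The strongest reply is that the row B without A may never occur. Protocol 2.2.1 reports no suspected PDSS in the earlier trial and considers the mechanism proposed for the pamoate product not relevant to TV-44749. Three cases would then be new data that raise concern, so B would bring A with it and both readings would agree for PDSS. This is a fair argument, but the text does not settle it. The protocol anticipates PDSS: it requires at least three hours of observation after injection, lists PDSS as an event of special interest and provides for adjudication. One could equally say that such cases are not previously unknown. If they always count, the first bullet adds nothing to the rule.

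A second reply is that the clause is permissive and follows discussion, and that the Sponsor can end the trial anyway under 10.5. That stands, and it limits the consequence. It does not make the written threshold mean what it appears to mean, and the same argument would make every rule in 7.4 unnecessary.

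A third reply is that *and* is only a list connector. That is plausible, but the evidence of intent is weak. A reader might cite Section 9.5, which mentions PDSS events as defined in the stopping criteria, as proof that separate conditions were intended. That reference points to the definition of an event, not to how the bullets combine. Nor does "one of the stopping rules in participants as detailed below (Section 7.4 of the study protocol) is met" in SAP 2.1 settle it, since it fits equally well with the whole last list being one rule.

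**Conclusion.** The point holds as a wording fault in a participant-safety rule. Read literally, three or more PDSS cases do not meet the last rule of 7.4 unless previously unknown safety data also become available, and no visible text makes the count sufficient by itself. Confidence in that reading is high. The practical consequence is modest and confined to PDSS that is nonserious or not judged drug-related. It shrinks further if three cases are themselves accepted as previously unknown data.

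A reader might infer that three PDSS cases could not lead to the trial being stopped, or that the Section 4.1 actions would be closed. The documents do not support either inference: the other lists in 7.4, the cohort 1A trigger in 4.1 and the Sponsor's discretion in 10.5 all remain. A reader might also take a plain *or* as pure clarification in line with the first list. It is not, because that list asks for issues that overturn the benefit-risk assessment, whereas the last list asks only for data that raise concern.

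The conclusion rests on the visible text; a standalone PDSS count in redacted 8.3.8 or in Table 8 would change it.

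**What to change.** Reword the last list of 7.4 so that three or more participants meeting the PDSS definition, counted cumulatively over all cohorts, is sufficient alone. There are two ways to do this.

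- **Preferred:** list the PDSS count as its own stopping criterion. The existing conjunction then adds nothing, because the count already suffices, and can be removed. The new-data bullet should not be left as the only item in the list by accident, since it would then suffice alone. It can be dropped in favour of the first list's benefit-risk item or kept deliberately.
- **Alternative:** introduce the list with *if any of the following occur* and replace *and* with *or*. The amendment should then state that previously unknown data raising a safety concern also suffices alone, and that this is a lower bar than the first list sets.

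Either way the clause can stay permissive and keep the prior discussion between Sponsor and Investigator. Sections 4.1 and 9.5 and SAP 2.1 already point to the stopping rules and need no edit. The cost is a short wording change in the next protocol amendment, with no effect on the SAP, design, data collection or analysis.

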8. TRIAL ASSESSMENTS AND PROCEDURES

8.1. Screening/Baseline Assessments and Procedures

A signed and dated ICF will be obtained before screening procedures commence (Section 10.3). Evaluations obtained as part of routine medical care and performed during the screening period may be used in place of the protocol-specific evaluations. Participants will acknowledge and agree to the possible use of this information for the trial by giving informed consent. Participants will be provided with the option to provide a sample for pharmacogenomics analyses during period 3. A separate written informed consent will be obtained from each participant before pharmacogenomics samples will be collected.

After informed consent is obtained, participants who are screened will be assigned an 8-digit permanent identification number such that all participants from each investigational center are given consecutive identification numbers in successive order of inclusion. The first two digits of the screening number will be the number assigned to the country where the investigational center is located, the next 3 digits will be the designated Investigator center number, and the last 3 digits will be assigned at the Investigator center (eg, if the number assigned to the country is 01, the third participant screened at center 5 would be given the number of 01005003).

The screening period will take place within 40 days prior to the antipsychotic's 3-day WO period. Screening procedures and assessments may be performed at any time during the screening period. Confirmation of eligibility for the trial will be performed on day 3 and determined based on an abbreviated list of eligibility criteria using laboratory and clinical scale values collected on day 1. If, due to technical reasons, laboratory results are not available by day 3, eligibility may be confirmed on day 4, prior to dosing ([Table 1](#)).

Participants who meet the inclusion criteria and do not meet the exclusion criteria at the screening visit may be enrolled in the trial.

